5.2.3. Analyses for Categorical Data

For categorical variables (such as Subject and HCP questions), the counts and percent of subjects responding to each category will be presented.

5.3. Methods to Manage Missing Data

Subjects with missing value for a given efficacy variable will not contribute to the analysis of that variable.

6. ANALYSES AND SUMMARIES

All efficacy summaries and analyses will be conducted within the FAS population. Analyses will be primarily descriptive in nature. No interim analyses are planned.

6.1. Analysis of Primary Endpoint

The primary endpoint is the mean percent of home self-injections that were successfully administered (ie, combined across visits). Each subject will have a maximum of 3 home self-injections, each of which will be defined as a success or failure. A success is defined as a home self-injection that was successfully performed by the study participant at home and on schedule (13 week interval ± 1 week). If the subject attempts but is unable to administer the self-injection at home and had it performed instead at the clinic, then that attempted self-injection would be classified as a failure. If a subject discontinues from the study prior to attempting all 3 home self-injections, or chooses not to attempt an injection at home, but has it performed in the clinic, then only the injections that were attempted at home will be evaluated and included in the analysis; ie, all attempts are included in the denominator. When several home attempts occurred at a visit, the last attempt is counted at a visit.

These binary outcomes are correlated within the subject, and they will therefore be analyzed with a GEE model for clustered binomial data, using subject as the clustering variable. The GEE model for this single-group analysis will use the logit link and working correlation structure of independence. This GEE model will include only the intercept term and is used to obtain a 95% CI based on standard error estimates that take into account the correlation of binary observations within the patient; the point estimate and 95% CI for the intercept will be back-transformed (anti-logit transformation) to obtain the point estimate and 95% CI on the proportion scale. The proportion estimate and 95% CI will be subsequently multiplied by 100 to obtain results on the percent scale. Note that proportion estimate from the GEE model equals:

Proportion of attempted self-injections successfully administered at home= (total # of successful home self-injections) / (total # of home self-injection attempts).

A sensitivity analysis will be conducted for the primary endpoint; this analysis will exclude primary endpoint data for sites who required closure during study due to Good Clinical Practice violations.

6.2. Analysis of Secondary Endpoint(s)

The secondary endpoint is the continuation rate for the method at 1 year. This is similar to the primary endpoint in study GA67815.1

The number and percentage of subjects completing 0 months (receiving first injection), 3 months (receiving first and second injections), 6 months (receiving first, second and third injections), and 9 months (receiving all 4 injections but not returning for follow-up visit) will be summarized. Subjects had completed 12 months if they received all 4 injections, had a follow-up visit and were not recorded as discontinuing during the 12 month period.

The continuation rate equals:

(# subjects who have not discontinued by 12 months) / (total # of subjects in study).

The total proportion of subjects who have not discontinued by 12 months (the follow-up visit) will be estimated along with a 95% confidence interval (CI), calculated using the normal approximation to the binomial.

6.4. Correlation Analyses

To describe the degree of relationship between the subject educational level to the subject's rating of the usefulness of training materials (based on Question 1 and Question 2 of subjects questionnaire), an analysis of correlation will be performed between these two categorical variables, the chi-square test and the resulting p-value, as well as the Cramér's V (φ_c) will be reported as a measure of correlation between these two variables.

6.5. Subset Analyses

No subset analysis are planned for this study.

6.6. Baseline and Other Summaries and Analyses

6.6.1. Baseline Summaries

All demographic, baseline characteristics and pre-treatment conditions will be summarized using the safety population. Descriptive statistics, including number of patients, mean, standard error, median, and range for continuous variables, and frequency and percent for categorical variables, will be provided for all demographic, baseline characteristics, and pre-treatment conditions.

6.6.2. Study Conduct and Subject Disposition

The number and percentage of patients, enrolled and treated in the study will be presented, together with the number and percentage of patients who withdrew from the study or study medication prematurely. A breakdown of the corresponding reasons for premature withdraw from study or study medication will be provided.

A tabulation of the number and percentage of patients included in each analysis population will be provided. Reasons for exclusion from analysis population will also be provided.

Details on the subject disposition will be provided in subject listings.

6.7. Safety Summaries and Analyses

Safety data, consisting of all adverse events, including unplanned pregnancies, persistent injection site reactions, SAEs, premature discontinuations, concomitant medications, vital signs, height and weight, and laboratory parameters, will be tabulated and listed according to Pfizer's standard reporting algorithms.

6.7.1. Adverse Events

AE assessment will be performed at Screening, Baseline and Final Visits. During the "at home" portion of the study, study subjects will contact the clinic by phone after performing each self-injection to report any AEs, including unplanned pregnancy (lack of efficacy) and injection site reactions.

In case the subject reports any injection site reactions, the clinic staff will collect detailed information about the reaction (eg, timing; persistence; appearance, is it getting worse or better; how large or deep is it; how bothersome, etc.). The physical examination at the end of study will allow evaluation of the injection sites, and investigators should determine any sequelae at the injection sites that may be due to a persistent injection site reaction and report them as AEs or serious adverse events (SAEs) accordingly.

Adverse events will also be summarized by injection method (ie, Self-injection at home, Supervised self-injection at clinic by health care provider and Other injections (including the injection performed by a friend).

An adverse event is considered treatment emergent relative to a given treatment if:

- The event occurs for the first time during the effective duration of treatment and was not seen prior to the start of treatment (for example, during the baseline or run-in period), or
- The event was seen prior to the start of treatment but increased in severity during treatment.

AE reporting timeframe for this study will be 14 weeks after the last injection, or until the end of study visit, whichever is the earliest.

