3. STUDY DESIGN

This is an open-label, single-arm, 1-year study to assess home self-administration of Sayana Press in women who desire long-acting reversible contraception (LARC), are interested to attempt DMPA self-injection at home and are judged by their HCP to be good candidates for the self-injection option. Following training and a supervised initial self-injection at the clinic, study participants will self-inject Sayana Press in the home setting every 3 months (at Month 3, Month 6 and Month 9) and return for a final study visit at Month 12.

Approximately one hundred sixty (160) adult women subjects of reproductive age (18 to 45) will be enrolled at approximately 10 study centres in the UK (and other countries in Europe if required) with approximately 16 subjects per study centre, to ensure that at least 100 women will complete the study.

Participants will attend 2 or 3 study visits at the clinic: a Screening/Baseline Visit (or Screening and Baseline visits separately) and a Final Visit. At Months 3, 6 and 9, participants will be asked to contact the clinic by phone after performing each scheduled home self-injection in order to confirm the date of injection and to report any AEs, and/or injection difficulties or problems with the device. Should the injection site reactions occur, the centre staff will collect detailed information about these reactions. If at least 1 week has passed from the scheduled self-injection date and the clinic has not heard from the subject, the clinic staff will contact the subject to obtain the necessary information and provide appropriate instructions to the subject, depending on the circumstances. All AEs, including pregnancy and injection site reactions will be recorded on the AE Case Report Form (CRF) page. Reasons for self-injection failure will also be recorded in the CRF.

At the Month 12 Final Visit or Premature Discontinuation, subjects will be asked to complete the CCI

If a subject does not perform a scheduled self-injection at home for any reason, the subject should immediately contact the clinic to explain the reason why the injection was not performed. The HCP at the clinic must provide instructions to the subject regarding how the scheduled injection will be provided:

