Study subjects will self-inject Sayana Press at home according to schedule (13 week interval +/- 1 week). They will be asked to contact the clinic by phone after performing each self-injection in order to confirm the date on which the injection was performed and report any AEs, including unplanned pregnancy, concomitant medications and injection site reactions. During this phone call, the clinic staff will also record whether the subject had any difficulties in performing the injection or had problems operating the device and what those issues were. In case the subject reports any injection site reactions, clinic staff will collect detailed information about the reaction (eg, timing; persistence; appearance; is it getting worse or better; how large or deep is it; how bothersome, etc.). All AEs, including unplanned pregnancy and injection site reactions will be recorded on AE CRF page. Reasons for self-injection failure will also be recorded in the CRF.

If a participant fails to contact the clinic to report the injection date, the study centre personnel shall not contact the patient until after the treatment window (+/- 1 week) for that planned injection has expired. If at least 1 week has passed from the scheduled self-injection date and the clinic has not heard from the subject, the clinic staff will contact the subject to obtain the necessary follow-up information and provide appropriate instructions to the subject, depending on the circumstances.

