7.2. Assessments Questionnaires

7.3. Safety Assessments

Vital Signs

Vital signs including heart rate, sitting systolic and diastolic blood pressure will be taken at Screening, Baseline and Final Visits.

Weight and Height

Weight and height measurements will be conducted at Baseline and Final Visit.

General Physical Examination

General physical examination, including general appearance, vascular, nervous system, cardiovascular system and gastrointestinal system will be conducted at Screening and at the Final Visit.

Adverse Events Assessment

AE assessment will be performed at Screening, Baseline and Final Visits. During the "at home" portion of the study, study subjects will contact the clinic by phone after performing each self-injection to report any AEs, including unplanned pregnancy and injection site reactions. In case the subject reports any injection site reactions, the clinic staff will collect detailed information about the reaction (eg, timing; persistence; appearance, is it getting worse or better; how large or deep is it; how bothersome, etc.). The physical examination at the end of study will allow evaluation of the injection sites, and investigators should determine any sequelae at the injection sites that may be due to a persistent injection site reaction and report them as AEs or serious adverse events (SAEs) accordingly.

CCI	

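### The AE summary by injection method in SAP 6.7.1 is largely confounded with treatment period and AE ascertainment, so differences between methods cannot be read as effects of the method

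*SAP*

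**What the plan says.** SAP 6.7.1 plans the following display: "Adverse events will also be summarized by injection method (ie, Self-injection at home, Supervised self-injection at clinic by health care provider". A third category takes other injections, such as one given by a friend. The section does not split the display by injection number or separate the Day 1 dose. It names no denominator and has no rule for linking an event to an injection.

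The order of methods is fixed by design. Protocol 3 says: "Following training and a supervised initial self-injection at the clinic, study participants will self-inject Sayana Press in the home setting every 3 months", that is, at Months 3, 6 and 9. Under Protocol 4.5, women not approved after the first injection are discontinued.

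AE collection follows the same order. SAP 6.7.1 says "AE assessment will be performed at Screening, Baseline and Final Visits". Between those visits, "study subjects will contact the clinic by phone after performing each self-injection to report any AEs". Protocol 7.3 adds, "The physical examination at the end of study will allow evaluation of the injection sites". The same examination applies at premature discontinuation (Protocol 6.2). The AE window closes at the earlier of two limits: "14 weeks after the last injection, or until the end of study visit".

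**The concern.** Protocol 1.2 describes a study required by the regulator and names inability to inject properly as a principal risk of unsupervised use. A reader will look to this table to see whether home injection brings more injection-site problems than supervised injection.

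The table cannot answer that. Its two main categories differ in method, in time on drug, in how events are picked up, and in part in who contributes. A change in AE risk after the first dose, or a change in detection, would look the same as an effect of injecting at home. This could raise a false concern about home use or hide a real one.

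**Working it through.** The documents give no AE rate or by-method figure, so there is no stated result to reproduce.

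**1. Timeline for a woman who follows the schedule.** The home rule is "Study subjects will self-inject Sayana Press at home according to schedule (13 week interval +/- 1 week"), so the Month 3 dose falls 12 to 14 weeks after Day 1: 12 × 7 = 84 to 14 × 7 = 98 days.

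| Dose | Method | AE contact at or after the dose | Next scheduled AE contact |
|---|---|---|---|
| Day 1 | Supervised, clinic | Staff present; Baseline AE assessment | Month 3 call, about 84 to 98 days later |
| Month 3 | Home | Call after injection | Month 6 call |
| Month 6 | Home | Call after injection | Month 9 call |
| Month 9 | Home | Call after injection | Final Visit, with site examination |

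For the calls, Protocol 6.2 says "They will be asked to contact the clinic by phone after performing each self-injection". The Month 3 call comes after the second dose, so an event reported then could belong to either dose. SAP 6.7.1 does not say which. In completers the examination falls in the Month 9 interval. In a woman who stops before Month 3 it can fall in the Day 1 interval.

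**2. How much of the clinic category is Day 1.** From the documents: 160 enrolled. Assumed: all 160 receive the Day 1 dose; 130 are approved with 2.6 later injections each (130 × 2.6 = 338); a share c of these is given at the clinic. Day 1 share = 160 / (160 + 338c).

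- c = 0.02: 160 / 166.8 = 96%
- c = 0.05: 160 / 176.9 = 90%
- c = 0.11: 160 / 197.2 = 81%
- c = 0.20: 160 / 227.6 = 70%

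This pools all clinic injections. If doses given by staff are counted as other injections, the Day 1 share of the supervised category is higher.

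**3. Why the denominator matters.** Supervised Day 1 exposure is 160 × 13 = 2,080 weeks. Home exposure runs from 3,900 weeks (only 100 women inject at home, 3 times each: 300 × 13) to 6,240 weeks (no dropout: 480 × 13), which is 1.9 to 3.0 times as much. With the same AE probability q in every interval, the share of women with at least one event is q over one supervised interval and 1 − (1 − q)³ over three home intervals:

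- q = 5%: 5% against 14.3%
- q = 10%: 10% against 27.1%
- q = 20%: 20% against 48.8%

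Per injection, the same inputs give a ratio of 1.00.

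**4. Per-injection home/supervised ratio with no method effect** (all inputs assumed).

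- Constant risk, equal capture: 1.00
- True risk falls from 15% in the first interval to 10% later: 0.10 / 0.15 = 0.67
- Capture 70% in the first interval, 100% later: 1.00 / 0.70 = 1.43
- Capture 100% in the first interval, 70% later: 0.70 / 1.00 = 0.70

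**5. The site examination, as an illustration.** Suppose the calls find a fraction s of lasting site reactions and the examination finds 95% of those from the Month 9 dose only (assumed). For completers the ratio is ((2s + 0.95) / 3) / s.

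- s = 0.4: 0.583 / 0.4 = 1.46
- s = 0.6: 0.717 / 0.6 = 1.19
- s = 0.8: 0.850 / 0.8 = 1.06

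If lasting reactions persist and the examination finds them equally well at every earlier site, detection is equal and the ratio is 1.00.

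**The case against.** The strongest reply is that no comparison is planned. SAP 5.1 says there are no treatment comparisons and that everything is descriptive, and neither visible objective is comparative safety. That is true, but it does not tell a reader how to take a table laid out by method, and SAP 6.7.1 carries no caveat.

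A reader might infer that the two rates must differ by construction. The documents do not support that. Percentages of women would differ because exposure differs, but SAP 6.7.1 does not say that percentages of women will be used, and per-injection rates can be equal.

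A reader might also infer that closer follow-up pushes site events towards home. That is one possibility. Staff watch the Day 1 injection and assess AEs at that visit. The post-injection call has no set timing, and under Protocol 6.2 staff do not chase it until the window has closed. Women are told to monitor each site until the next injection (Protocol Appendix 2). A falling risk with time would lower the home rate. The ratios of 1.46, 1.19 and 1.06 let the final examination see only the Month 9 site, whereas Protocol 7.3 and SAP 6.7.1 speak of injection sites in the plural.

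SAP 6.3 is not visible. The amendment log says its endpoints are summarised by visit, so some separation of Day 1 may exist there. The by-method AE summary in 6.7.1 is logged as a separate change, and its own text has no such split. SAP 6.7 also refers to the sponsor's standard reporting algorithms, which are not in the documents and may set a denominator. Neither would remove the alignment of method with period in the 6.7.1 display.

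Finally, post-baseline home against clinic is not a clean replacement. Clinic doses come from women who could not, or chose not to, inject at home (Protocol 3 and 9.2.1), and they involve a face-to-face visit. This objection stands and limits what the fix can claim.

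**Conclusion.** The point holds as confounding. As written, SAP 6.7.1 gives a table in which the supervised category is mainly the first treatment interval and the home category is only later ones, with different AE ascertainment in each. By-method differences cannot be read as method effects. The split is not total, because later clinic injections are allowed.

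The Day 1 share of 70% to 96% rests on the assumed retention and clinic use. The per-injection range of 0.67 to 1.43 shows that the bias could go either way. The ratios of 1.46, 1.19 and 1.06 are illustrations under assumed detection rates, not estimates. The documents do not show that home rates will be inflated. The change is worth making because it is cheap and alters what the table can support.

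**What to change.** In SAP 6.7.1:

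- Show the Day 1 supervised injection as its own row, separate from post-baseline injections by method (home self-injection, supervised clinic self-injection, other). State where doses given by clinic staff are counted.
- Assign each AE by onset date to the preceding injection, and report per injection.
- Flag events first found at the final or premature discontinuation examination, and give the figures with and without them.
- State that Day 1 is not a comparator for home injection, and that post-baseline clinic injections are few and selected, so that contrast is descriptive only.

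The cost is SAP wording and one table shell, with no change to trial conduct. Injection dates, clinic injections and the timing of site reactions are already collected (Protocol 3 and 6.2). The sponsor should confirm that the AE page holds onset dates and shows at which contact an event was first reported. The downside is a small, imprecise post-baseline clinic row: about 7 to 68 injections (338 × 0.02 to 338 × 0.20) under the assumptions above.

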- g. Whenever a scheduled injection has been delayed beyond the protocol-specific window (scheduled injection date ± 1 week), the subject should be advised to contact the clinic and speak to a healthcare professional regarding the need to exclude pregnancy before any additional injections, advice regarding additional contraception, and also for the timing of the next injection. A pregnancy test is to be conducted if the Sayana Press injection is delayed outside the protocol study drug administration window. This could be either a home pregnancy test or test conducted in the clinic. If the subject has a positive pregnancy test result, she is not to inject Sayana Press and must inform the study centre immediately, to conduct a final study visit (subject will be prematurely terminated). The study centre must complete and submit an Exposure During Pregnancy Form to Pfizer within 24 hours of awareness of the pregnancy. The study centre will follow all protocol required pregnancy in utero procedures (See Section 8.10).
- h. AEs (serious and non-serious) should be recorded on the case report form (CRF) from the time the subject has taken at least 1 dose of investigational product through the last subject visit.

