8.2. Reporting Period

For SAEs, the active reporting period to Pfizer or its designated representative begins from the time that the subject provides informed consent, which is obtained prior to the subject's participation in the study, ie, prior to undergoing any study-related procedure and/or receiving investigational product, through and including 28 calendar days after the last administration of the investigational product. SAEs occurring to a subject after the active reporting period has ended should be reported to the sponsor if the investigator becomes aware of them; at a minimum, all SAEs that the investigator believes have at least a reasonable possibility of being related to investigational product are to be reported to the sponsor.

AEs (serious and non-serious) should be recorded on the case report form (CRF) from the time the subject has taken at least 1 dose of investigational product through the last subject visit.

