3.5. Safety Endpoints

Adverse events (AEs), including unplanned pregnancy and persistent injection site reactions, premature discontinuations, concomitant medications, vital signs and laboratory parameter (urine pregnancy test).

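### The 14-week AE cut-off in SAP 6.7.1 can be shorter than the protocol's recording period and can leave pregnancies found by the delayed-injection test out of the AE summaries

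*SAP*

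**What the plan says.** SAP 6.7.1 sets the AE period: "AE reporting timeframe for this study will be 14 weeks after the last injection, or until the end of study visit, whichever is the earliest". Its parent section, SAP 6.7, describes the safety data to be tabulated and listed as "consisting of all adverse events, including unplanned pregnancies, persistent injection site reactions", with no time limit. SAP 3.5 lists as safety endpoints "Adverse events (AEs), including unplanned pregnancy and persistent injection site reactions".

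Protocol 8.2 has AEs recorded on the CRF "from the time the subject has taken at least 1 dose of investigational product through the last subject visit", and footnote h of the Schedule of Activities repeats this. Protocol 8.2 also has a separate period for active SAE reporting to the sponsor, "through and including 28 calendar days after the last administration of the investigational product". That is a different clock and does not explain the 14 weeks.

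On late injections, footnote g of the Schedule of Activities says: "A pregnancy test is to be conducted if the Sayana Press injection is delayed outside the protocol study drug administration window". It adds: "If the subject has a positive pregnancy test result, she is not to inject Sayana Press". The woman then has a final study visit and leaves the study. Under Protocol 6.2, centre staff do not contact a woman who has not reported her injection until that injection's window has closed.

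**The concern.** The SAP takes the earlier of two dates, so its AE period can equal the protocol's or be shorter, but never longer. The two differ only when the last visit comes more than 14 weeks after the last injection. A pregnancy found because an injection was missed is likely to fall there. Protocol 1.2 itself names a forgotten injection followed by contraceptive failure as a risk of home use, and the study was required by the regulator as a post-authorisation safety study.

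If the cut-off is applied as written, recorded pregnancies can be missing from the AE tables, and an omission can only lower the count. The SAP does not say whether a pregnancy is placed by conception, test or report date. It also does not say whether the injection window runs from the previous injection or from a calendar fixed at baseline. The count would depend on both.

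**Working it through.** **Inputs.** Interval 13 weeks, window ±1 week (Protocol 2.2, 6.2); cut-off 14 weeks (SAP 6.7.1); final visit at Month 12 ±1 week (Protocol 6.2), taken as week 52 ±1 because 4 × 13 = 52.

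**The cut-off.** 13 + 1 = 14 weeks = 14 × 7 = 98 days. The AE period ends on the day an injection is last on time, counted from the previous injection.

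**Delay-triggered tests, placed by test date.** The previous injection is assumed to have been inside its own window.
- *Month 3.* The previous injection is the baseline one, so under either anchor the window closes at day 98. The earliest delay-triggered test is day 99, so all are outside.
- *Months 6 and 9, window counted from the previous injection.* The same arithmetic applies (99 > 98), so all are outside.
- *Months 6 and 9, dates fixed from baseline.* Let the previous injection be u days after its scheduled date, u from −7 to +7. The window closes 98 − u days after it, which is 91 to 105 days (13 to 15 weeks). A test t days after closure is at day 98 − u + t, inside only if u ≥ t. With u uniform over the 15 days (an assumption), the share inside is 7/15 = 47% at t = 1, 1/15 = 7% at t = 7, and 0 from t = 8.

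A positive test stops the next injection, so the cut-off stays where it is.

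**The same tests, placed by onset.** The event is inside if test day minus lag ≤ 98, where lag is the time from onset to test.

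| Test day | Lag needed to be inside |
|---|---|
| 99 | at least 1 day |
| 112 | at least 14 days |
| 140 | at least 42 days |

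Promptly tested pregnancies mostly stay inside; later-detected ones may not.

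**No Month 9 injection, but the woman stays to the final visit.** With the Month 6 injection at week 26, the cut-off is 26 + 14 = week 40. The final visit is at weeks 51 to 53, so 51 − 40 = 11 to 53 − 40 = 13 weeks lie outside, whichever date is used.

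**Completers.** With the last injection at week 39 and the visit at weeks 51 to 53, the gap is 12 to 14 weeks and nothing is lost. For variable timing I enumerated P(gap > 98 days) by day, with injection and visit deviations uniform over the same spread (an assumption). The gap is 91 + v − u for dates fixed from baseline, and 91 + v − (u1 + u2 + u3) for chained intervals with the visit fixed to baseline.

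| Spread | Fixed from baseline | Chained |
|---|---|---|
| ±3 days | 0% | 2.9% |
| ±7 days | 12.4% (mean excess 3.0 days) | 20.0% (mean excess 5.1 days) |

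At ±7 days the mean loss over all completers is 0.373/364 = 0.10% (fixed) to 1.030/364 = 0.28% (chained) of follow-up.

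**Scale of one event.** The documents give no pregnancy rate, so no expected count can be derived. One omitted pregnancy among 160 women is 1/160 = 0.6 percentage points.

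**The case against.** The best defence is that SAP 6.7.1 is a specific rule under a general heading. It directly follows the treatment-emergent definition, and 13 + 1 weeks is a recognisable on-treatment period. SAP section 2 lets the SAP modify the protocol, and Protocol 8.2 governs recording, not tabulation. This reading is available, but neither section states it, and the definition does not tie its treatment duration to 14 weeks. The clash with SAP 6.7 is therefore an unreconciled pair of statements, not a proven contradiction.

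The treatment-emergent wording also points to onset, not detection, and by onset many promptly found pregnancies stay inside. That stands. A reader might infer that the SAP drops every pregnancy found by a delayed-injection test. The documents do not support this, because it needs test or report dating and, at Months 6 and 9, windows chained from the previous injection.

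A reader might also infer that Protocol 8.2 always captures these pregnancies. That assumes the woman attends a final visit, and Protocol 6.4 anticipates non-return. For a woman who never returns, the last subject visit is itself unclear.

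Nor are pregnancies lost to the trial. They go to the sponsor on SAE and EDP forms (Protocol 8.10). Lack of efficacy is reportable as an SAE (Protocol 8.6), and Protocol section 3 labels unplanned pregnancy as lack of efficacy. Urine pregnancy tests are a separate safety parameter (SAP 3.5), and withdrawal reasons are tabulated (SAP 6.6.2). SAP 6.3 is not visible, and a separate pregnancy summary there can be neither shown nor excluded.

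**Conclusion.** The concern holds in limited form. SAP 6.7.1 sets an AE period that can be shorter than the protocol's recording period, does not say how it relates to SAP 6.7, and visibly makes no exception for pregnancies. Pregnancies found by the delayed-injection test are the events most exposed. By test or report date, all are outside at Month 3, and at Months 6 and 9 if windows are chained; with dates fixed from baseline, up to 47% fall inside for a test one day after closure and none from eight days (uniform timing assumed). By onset, many remain.

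The defect is confined to the AE summaries. Completers lose nothing on the nominal schedule and at most about 0.3% of follow-up under the widest spread examined. The primary and secondary endpoints are not affected. It is still worth correcting, because any omission lowers the count of a named safety endpoint.

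**What to change.** In SAP 6.7.1, replace the cut-off with a rule to this effect:
- All AEs recorded on the CRF from first injection through the last subject visit, or last contact if there is no final visit, are tabulated.
- The tabulation is split at ≤14 and >14 weeks since the last injection.
- Every unplanned pregnancy is counted whatever its date, with the test date and, where available, the estimated conception date listed.
- The 28-day SAE active reporting period in Protocol 8.2 does not limit this tabulation.

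The cost is SAP wording and one extra column. AEs are already recorded through the last visit, so no protocol change is needed. The documents do not show conception date as a CRF item, hence its listing only where available. The downside is that some events beyond the dosing interval enter the tables; the split makes them visible and keeps the on-treatment view.
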